# Study Protocol and Statistical Analysis Plan

Official title: Analgesic Effect of Ropivacaine Combined with Methylene Blue in Fascia Iliaca Block for Patients

Undergoing Hip Arthroplasty

NCT number: NCT06284941

Date: December 24, 2024

For inclusion in this study, patients of either sex had to meet the requirements for hip replacement surgery, be in the age range of 65–85 years, have a body mass index (BMI) in the range of 18–28 kg/m², be categorized as American Society of Anesthesiologists (ASA) grade II to III, have no history of analgesic or local anesthetic allergies, and have no history of alcoholism or narcotic drug abuse. Patients were excluded if they met any of the following criteria: refusal by patient or family member to participate in the study, having a serious mental illness or inability to communicate clearly with researchers, severe coagulopathy, allergy to local anesthetics, severe psychiatric illness or other communication disorder, history of neurological disease such as Guillain-Barré syndrome, infection at the puncture site, delay in awakening post-surgery for more than 60 min, post-surgical use of an analgesic pump, and inability to follow-up at the required time points.

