### Randomization and Blinding

Using a computer-generated random sequence, a person who was not involved in the experimental operation divided the patients into two groups in which FICB was achieved with either methylene blue and ropivacaine (MB+R group) or ropivacaine only (R group). All serial numbers were encoded sequentially, kept, and scheduled for each experiment by someone other than the researcher. Because methylene blue is a blue liquid, exposure to the color could expose the experimental group. Thus, blinding was achieved by having different researchers perform different steps in the study to avoid the color affecting the experiment. The steps of the experimental procedure,

including the extraction of the liquid medicine, performance of the nerve block, and postoperative follow-up, were performed by different anesthesiologists, who were only responsible for independent experimental procedures, did not know the information about the patient outside the experiment, and did not communicate with each other about the patient and the experiment. Catheterization was not performed for any patient to prevent the color of the urine from exposing the experimental group.

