#### **Operative Procedures**

Nerve Block

Before general anesthesia induction, FICB was performed under ultrasound guidance using the Edge II ultrasound device (Sonosite, USA). With the patient in supine position and the surgical area disinfected, the high-frequency ultrasound probe was placed perpendicular on the inguinal ligament. The probe was slowly moved until the "bowtie sign" created by the internal oblique and sartorius muscles was observed. This sign corresponds to the confluence of the fascia lata and fascia iliaca, which represents the fascia iliaca compartment. With an in-plane technique in the caudal to cranial direction, the needle tip was inserted deep to the fascia iliac. After confirming it could be withdrawn without blood, local anesthetic drugs in a volume of 30 ml were injected. Patients in the MB+R group received 0.25% ropivacaine (Product Batch Number: EE2344, Zhejiang Xianju Pharmaceutical Co., Ltd.) and 0.05% methylene blue (Product Batch Number: 2310032, Jichuan Pharmaceutical Group Co., Ltd.), and those in the R group received only 0.25% ropivacaine (same batch number).

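### The allergy criteria do not name methylene blue, the only drug that differs between the arms, so a patient with a known reaction to it is eligible as written

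*Combined protocol and SAP*

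**What the plan says.** Allergy appears twice in the eligibility text of the opening section. Among the inclusion criteria, patients must "have no history of analgesic or local anesthetic allergies, and have no history of alcoholism or narcotic drug abuse". Among the exclusions the list runs "severe coagulopathy, allergy to local anesthetics, severe psychiatric illness or other communication disorder". Local anesthetic allergy is therefore covered twice and analgesic allergy once.

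Under Randomization and Blinding, the two groups are those in which "FICB was achieved with either methylene blue and ropivacaine (MB+R group) or ropivacaine only (R group"). Under Operative Procedures, Nerve Block, "local anesthetic drugs in a volume of 30 ml were injected". "Patients in the MB+R group received 0.25% ropivacaine" "and 0.05% methylene blue (Product Batch Number: 2310032, Jichuan Pharmaceutical Group Co., Ltd".), while the R group received ropivacaine alone at the same strength and from the same batch.

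The blinding section also gives drawing-up, block and follow-up to separate anesthesiologists. It says that they lacked patient information beyond the experiment and did not discuss the patient with one another.

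**The concern.** One would expect allergy screening to cover at least the drug under test. Here it covers, twice, a class of drug that both arms receive, and does not mention the one that only MB+R patients receive. If the written criteria are the whole of the screen, a person known to react to methylene blue is not stopped by them, and the exposure would be avoidable.

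The division of labour used for blinding makes the screen more important. If the person injecting the solution has little information about the patient, a later check at the bedside cannot be assumed. Eligibility screening is then the only safeguard that the documents describe.

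**Working it through.** This is mainly a comparison of the eligibility text with the list of drugs. The plan states no figure of its own to reproduce.

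**Step 1. Match each drug to the allergy criteria.**

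| Drug | Arm | Inclusion criterion | Exclusion criterion |
|---|---|---|---|
| Ropivacaine | both | covered, as a local anesthetic | covered, as a local anesthetic |
| Opioids (at induction, during maintenance, and as supplemental analgesia) | both | covered, as analgesics | not listed |
| Methylene blue | MB+R only | not named | not named |

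**Step 2. Look for a general clause.** The other inclusion criteria concern the indication for hip replacement, age, body mass index, ASA grade, and alcohol or drug abuse. The other exclusions concern refusal, mental illness or communication, coagulopathy, neurological disease, infection at the puncture site, delayed awakening, use of an analgesic pump, and follow-up. None refers to allergy to study drugs in general, and none would catch a methylene blue reaction.

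**Step 3. Look for a later check.** The sections on randomization, operative procedures, outcomes and statistical methods contain no question or test about methylene blue allergy before injection.

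**Step 4. Trace one patient.** Take a patient with a documented methylene blue reaction, no analgesic or local anesthetic allergy, and all other criteria met. Steps 1 to 3 show nothing that excludes this patient. Randomisation can then allocate the patient to MB+R.

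**Step 5. Size of the exposure.** Inputs from Nerve Block: volume 30 ml; methylene blue 0.05%.

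- 0.05% weight by volume = 0.05 g per 100 ml = 0.5 mg/ml
- 0.5 mg/ml × 30 ml = 15 mg per MB+R patient, and 0 mg per R patient

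This assumes that 0.05% is the concentration in the final 30 ml mixture. The text does not say so outright, but it is the natural reading.

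**The case against.** **The wording could be stretched to cover methylene blue.** Nerve Block calls the injectate local anesthetic drugs, and the title concerns the analgesic effect of the combination. A lenient reader might therefore place methylene blue under analgesic or local anesthetic allergy. This shows that the text is open to more than one reading, but it does not close the gap. The same label is used for both arms' injectate, the protocol names methylene blue separately from ropivacaine wherever it describes the groups, and a patient asked about painkillers and local anesthetics may not think to mention a reaction to a dye.

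**The event is probably rare, and no analysis is shown to suffer.** This stands. A reader might infer that reactions would appear as a difference between arms in adverse events and distort the safety comparison. The documents give neither a reaction rate nor a sample size, so that cannot be sized, and for a rare event it is unlikely to move the comparison.

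**A wider gap in contraindications.** The blinding section says "Catheterization was not performed for any patient to prevent the color of the urine from exposing the experimental group", so the protocol expects some of the dye to reach the urine. A reader might infer that a broader set of conditions or medicines should have been screened for. The documents do not support that step. They contain no product labelling and no list of contraindications, and discoloured urine does not show which, if any, would matter at this exposure. The point is confined to known hypersensitivity.

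**It may be too late.** The text is in the past tense and gives batch numbers, so a reworded criterion may no longer change who was exposed. This also stands, and it changes the form of the remedy: disclosure rather than prevention.

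**Conclusion.** The point holds in a narrow form. The eligibility criteria do not match the list of study drugs: the one drug that distinguishes the arms is missing from the allergy screen, and no general clause makes up for it. A patient with a known methylene blue reaction is eligible on the written criteria and could receive about 15 mg, subject to the concentration assumption above.

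A reader might infer that the trial did expose such patients. The documents do not show this. They show only that the written rule permits it, and an unwritten check may have been made. No estimate, test or outcome definition is affected. The weight is that of a cheap improvement, made for safety and completeness.

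**What to change.** Reconcile the allergy criteria in the opening section with the drugs named under Randomization and Blinding and under Nerve Block. Replace the repeated local anesthetic item in the exclusions with known hypersensitivity to any study drug, naming methylene blue, and keep the inclusion wording. Apply the criterion to all candidates before randomisation, so that it acts equally on both arms and creates no selection difference between them.

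If enrolment is complete, state whether methylene blue allergy was asked about in practice, and report it as a limitation if it was not.

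The cost is one reworded line, one more question at screening, and perhaps a very few candidates lost. The analysis does not change.

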After successful nerve block, all patients were transferred to the operating room where they received routine monitoring of heart rate (HR), electrocardiogram (ECG), oxygen saturation (SpO2), etc. Radial artery puncture catheterization was performed under local anesthesia for invasive arterial pressure monitoring. For anesthesia induction, patients received an intravenous injection of propofol 1.0-2.0 mg/kg, rocuronium bromide 0.6 mg/kg, and sufentanil 0.2-0.3 µg/kg. The specifications of mechanical ventilation after endotracheal intubation were: tidal volume (VT) 6-8 ml/kg, respiratory rate (RR) 10–12 times/min, positive end expiratory pressure (PEEP) 3-5 cmH2O, and end-expiratory carbon dioxide partial pressure (PETCO2) 35~45 mmHg. Anesthesia was maintained by inhalation of 1.5%-2.0% sevoflurane along with intravenous infusion of remifentanil at 0.05-0.2 µg/kg/min and intermittent administration of rocuronium bromide 5-10 mg according to the intraoperative situation to maintain muscle relaxation. Blood pressure (BP) and HR fluctuation within 20% of baseline values was allowed according to the intraoperative situation. If BP dropped by >20% of the baseline value or if systolic BP was <90 mmHg, ephedrine 6 mg was given. If the HR was <50 beats/minute, an intravenous bolus of atropine 0.5 mg was given. All operations among included patients were performed by the same surgical team with the same surgical method, and the surgical method was hip replacement with posterolateral approach in the lateral decubitus position. The inhalation of sevoflurane and infusion of remifentanil was stopped 5 min before the end of the operation. After surgery, the patient was transferred to a recovery room, and

the endotracheal tube was removed once the patient was awake and spontaneous breathing had resumed. According to our pre-test experience, many patients refuse the use of analgesic pumps due to the relatively high cost, certain drug-related side effects, and the option of FICB. Thus, we did not include cases with post-surgical use of an analgesic pump in this study. In this study, fascia iliaca block was used to administer postoperative analgesia to patients. If the patients were not satisfied with the effect of fascia iliaca block, additional opioids were used for supplemental analgesia. At the same time, to avoid the effect of drugs on the level of patients' inflammatory factors, the use of non-steroidal analgesic drugs was prohibited.

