# Secondary Outcomes

As indicators of inflammation, the values of hypersensitive C-reactive protein

(hs-CRP), procalcitonin (PCT), and the neutrophil-to-lymphocyte ratio (NLR) also were recorded on postoperative days 1 and 2.

HR and mean arterial pressure (MAP) values were recorded at the following time points: operating room entry (T1), immediately before skin incision (T2), 1 min after skin incision (T3), skin suture (T4), and 30 min after extubation (T5). The requirement of supplemental analgesia was noted within 48 h postoperatively, along with the number of times patients got out of bed to perform activities within 48 h postoperatively and the distance walked after the patient's first attempt to get out of bed. Any occurrence of adverse reactions such as nausea, vomiting, and arrhythmia within 48 h postoperatively also was recorded. Any drug-related nerve damage after surgery was noted. Nerve deficits were defined according to sensory findings: 0—no nerve damage, 1—minor sensory paresthesia, 2—complete sensory parasthesia, 3—complete motor defect with or without sensory paresthesia, and 4—complex regional pain syndrome. Two researchers who were blinded to the group allocation assessed these outcomes.

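### Patients are excluded for slow awakening and post-surgical pump use, both seen only after the allocated block, and no analysis set keeps them

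*Combined protocol and SAP*

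**What the plan says.** The unnumbered eligibility paragraph gives one list of exclusions. Most are facts known at screening, such as coagulopathy, allergy or infection at the puncture site. The list ends with "delay in awakening post-surgery for more than 60 min, post-surgical use of an analgesic pump" and "inability to follow-up at the required time points".

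Under Randomization and Blinding, the two groups are defined by the block solution (MB+R or R). Under Operative Procedures, "Before general anesthesia induction, FICB was performed under ultrasound guidance".

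The same section returns to the pump. It reports from pre-test experience that "many patients refuse the use of analgesic pumps due to the relatively high cost, certain drug-related side effects, and the option of FICB", and concludes: "Thus, we did not include cases with post-surgical use of an analgesic pump in this study". An unsatisfactory block has its own route: "If the patients were not satisfied with the effect of fascia iliaca block, additional opioids were used for supplemental analgesia".

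The primary outcome is VAS at rest and with activity, before the block and at 2, 6, 12, 24 and 48 h after surgery. Among the secondary outcomes, "The requirement of supplemental analgesia was noted within 48 h postoperatively" and "Any occurrence of adverse reactions such as nausea, vomiting, and arrhythmia within 48 h postoperatively also was recorded".

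Statistical Methods gives summary statistics, tests and a 0.05 significance level. It names no analysis population, no rule for missing data and no sensitivity analysis.

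**The concern.** Randomisation protects a comparison only if the patients compared are those who were randomised. A rule that removes patients for something that happens after treatment can undo that protection, because the treatment may influence who is removed.

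A pump is itself analgesia, so its use may depend on pain, the primary outcome. It could also count as supplemental analgesia, so dropping pump users may drop secondary-outcome events. The protocol associates pumps with drug-related side effects, so the adverse-reaction comparison is exposed too. The effect depends on why patients are lost:

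- If losses are unrelated to pain and arm, only power is lost.
- If they follow pain under a rule common to both arms, a true VAS benefit is diluted and supplemental-analgesia rates are understated.
- If they differ by arm at the same level of pain, the bias can go either way and can create an effect where none exists.

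**Working it through.** **Order of events.** Allocation and block come first, then induction and surgery, then awakening, then any post-surgical pump. Every postoperative VAS score falls after this sequence has begun.

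- *Awakening delayed beyond 60 min* cannot be known before the block on any reading.
- *Post-surgical pump use*, as worded, is also observed only afterwards. An intention to use a pump could have been settled at screening, but no text says so.
- *Inability to follow up* is of the same kind if it means missed assessments. It may instead mean inability foreseen at enrolment; the text does not say.

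No section says that patients who meet these criteria after the block are followed, analysed or counted by arm.

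**Illustration of size.** The documents give no sample size, effect, SD or exclusion rate, so there is no figure of the plan's own to reproduce and every input here is assumed: one VAS score, normal, mean μ = 4 in R and 3 in MB+R, SD σ = 1.5, 40 per arm. Power and type I error come from 20,000 simulated trials per case, t-test at 0.05. Without exclusions the difference is 1.00 and power is 84%.

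Let c be the cut-off and p the share of patients above c who are excluded. Then:

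- α = (c − μ)/σ and q = 1 − Φ(α)
- mean of those above c: u = μ + σφ(α)/q
- mean of those kept: (μ − p·q·u)/(1 − p·q)

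For c = 5 and p = 1:

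- R: α = 0.667, φ = 0.3194, q = 0.2525, u = 5.898; kept mean (4 − 0.2525 × 5.898)/0.7475 = 3.359
- MB+R: α = 1.333, φ = 0.1640, q = 0.0912, u = 5.697; kept mean (3 − 0.0912 × 5.697)/0.9088 = 2.729
- Difference: 3.359 − 2.729 = 0.63

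| Excluded, same rule in both arms | Share lost, R / MB+R | Difference | Power |
|---|---|---|---|
| Random 10% | 10% / 10% | 1.00 | 79% |
| Random 20% | 20% / 20% | 1.00 | 75% |
| All above VAS 5 | 25.2% / 9.1% | 0.63 | 55% |
| Half of those above 5 | 12.6% / 4.6% | 0.86 | 74% |
| All above VAS 6 | 9.1% / 2.3% | 0.81 | 73% |
| Half of those above 6 | 4.6% / 1.1% | 0.91 | 79% |
| A quarter of those above 6 | 2.3% / 0.6% | 0.96 | not simulated |

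**No true effect (4 vs 4), unequal loss above VAS 5.** Losing 25% of these patients in R and 50% in MB+R gives kept means of 3.872 and 3.726, a false difference of 0.15 and a type I error of 6.9%. Losing 0% and 50% gives 0.27 and 12.2%. Swapping the arms reverses the sign. Equal loss of 50% leaves the error at 4.8%.

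**Supplemental analgesia.** Suppose it is needed above VAS 4: 50.0% in R and 25.2% in MB+R.

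- Deleting all above VAS 5: (0.500 − 0.2525)/0.7475 = 33% and (0.2525 − 0.0912)/0.9088 = 18%
- Deleting half of them: 43% and 22%

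**Keeping pump users.** If a pump brings everyone above VAS 5 to a value v, each arm's mean is μ − q·u + q·v. For v = 3 this is 3.268 in R and 2.754 in MB+R, a difference of 0.51. For v = 4 it is 0.68 and for v = 5 it is 0.84. Retention does not restore 1.00.

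**Weaker link between pain and exclusion.** The cases above with a VAS cut-off let the analysed score itself decide who can be excluded. As a separate check with no true effect, suppose the top 10% in R and 2% in MB+R are removed on a variable that correlates ρ with pain. The shift is 0.15 SD at ρ = 1, 0.07 SD at ρ = 0.5 and 0.04 SD at ρ = 0.3.

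**The case against.** The strongest reply is that pump use was elective. The protocol attributes refusal to cost, side effects and the availability of the block, and patients dissatisfied with the block received opioids and stayed in. The pump sentence could then describe whom the trial planned to enrol, and patients screened out before randomisation cause no bias. This reading is possible, but the criterion is worded as post-surgical use, the reasons given explain refusal rather than use, and nothing says the choice was fixed before allocation.

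Second, the one criterion that is post-treatment on every reading, slow awakening, has the weaker link to VAS, and the high-pain scenarios do not model it. That is fair. It limits what can be said about size for that criterion, but the exclusion still follows treatment.

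Third, the scenarios are severe. A pump decision need not track each of the rest and activity scores at five postoperative times, and a weaker correlation shrinks the shift, as shown. Separate staff for drug preparation, block and follow-up, together with blinded assessors, also make arm-dependent losses at equal pain less likely. They do not prevent pain-driven losses from differing if the two blocks work differently, which is what the trial tests. Blinding of patients is not stated.

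Finally, the text is in the past tense, so conduct may be complete. The analysis set and the reporting of exclusions can still be changed, using whatever data were recorded.

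**Conclusion.** The concern holds. A stated rule removes patients on events that follow the allocated treatment, and no analysis set keeps them. This rests on the order of events and on no assumed number, and confidence in it is high. It must be fixed, because it decides whether the primary comparison is a randomised one.

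That the VAS results are biased is not shown, only that they may be. Under the assumed inputs, consequences run from none beyond a loss of 5 to 9 percentage points of power, through dilution of a true difference of 1.00 to between 0.63 and 0.96, to a false difference of 0.15 to 0.27 with type I error of 7% to 12%. Without exclusion counts by arm and reason, one cannot tell which case applies.

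**What to change.** - Restrict the exclusion criteria to facts known before randomisation. If intended pump use or inability to attend follow-up is to be screened, ask before randomisation; if this was done, say so.
- Make the primary analysis all randomised patients in their allocated group.
- Record slow awakening and post-surgical pump use as post-randomisation events. Report pump use by arm and reason and include it in the supplemental-analgesia outcome, with a sensitivity analysis separating elective from pain-driven use.
- State how missed VAS time points are handled, with a method that keeps the patient's other data, such as a likelihood-based repeated-measures model.
- Keep the analysis with exclusions as a sensitivity analysis, and report exclusions by arm and reason.

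The cost is wording, plus recording VAS and the other outcomes in patients who would have been dropped; the documents do not say whether their data were collected. The drawback is that VAS under pump analgesia may dilute the difference, in one assumed case below the value under exclusion (0.51 against 0.63), so it must be read together with the supplemental-analgesia outcome. The gain is a comparison of the groups as randomised, not a larger difference.
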